4. **Research Plan:** Summarize the study design and research procedures using non-technical language that can be readily understood by someone outside the discipline. **Be sure to distinguish between standard of care vs.** research procedures when applicable, and include any flowcharts of visits specifying their individual times and lengths. Describe the setting in which the research will take place.

Overview of Study Design

This single-site, proof-of-concept, clinical trial is a double-blind, placebo-controlled, parallel group study to test the effectiveness of naltrexone + bupropion (NB) pharmacotherapy in BED patients with and without obesity. BED patients with (BMI > 30 and <50) and without obesity (BMI >21.5 and <29.9), will be randomized to NB (32 mg/day naltrexone combined with 360 mg/day bupropion) or placebo (n=50 per cell, n=200 total).

Following eligibility screening and randomization, participants will start a 12-week medication treatment period, a treatment period consistent with other BED medication trials (McElroy et al., 2016). Participants will have four weeks of up-titration: one tablet daily (Naltrexone 8mg/ Bupropion 90mg; 1 week), then two tablets daily (Naltrexone 16mg/ Bupropion 180mg; 1 week), then three tablets daily (Naltrexone 24mg/ Bupropion 270mg; 1 week), to reach the full dose of four tablets daily (Naltrexone 32mg/ Bupropion 360mg). The dosage will continue for the remainder of the 3 months. Medication will be discontinued at the end of 3 months, and patients will then be followed 12-months post-treatment to assess the durability of medication effects. The primary outcome measure is reduction in binge-eating frequency.

To evaluate correlates and mechanisms of NB on eating behavior, assessments will occur in the laboratory and in the field to optimize internal and external validity. Participants will complete human laboratory sessions ("lab sessions") before the start of medication and then during the final week of the 12-week medication period to evaluate the ability to resist eating preferred high-caloric food and subsequent overeating. During the laboratory sessions, we will evaluate potential mechanisms including eating peptides

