# Assessments.

Figure 2. Grid depicting when each assessment is obtained

rigare 2. Oria acpioning	when each assessment is obtained		Р	RE	DURING TREATMENT			Follo	OW-UP			
MEASURE	INSTRUMENT AND REFERENCES	Түре	BASELINE	LAB #1	WEEK 2	MONTH 1	MONTH 2	MONTH 3	LAB #2	6 Момтн	12 Month	BIOSENSOR
Screening Measures							ı		1			
Axis I Disorders	MINI Psychiatric Interview	Interview	*									
Binge-Eating Disorder	EDE Interview	Interview	*					*		*	*	
BMI	Weight, height	RA Eval	*	*	*	*	*	*	*	*	*	
Metabolic Measures	Lipids, HbA1c TSH (as needed)	Blood	*	*					*	*	*	
Safety Measures	Urine screen for pregnancy Urine drug test for opiates	Urine	*									
Menstrual Cycle Data	Menstrual cycle calendar, hormone use, reproductive and gynecological status	Interview	*		*	*	*	*		*	*	
Medical History	Clinical data, incl. start of new treatments	Interview	*					*			*	
Eating Behavior & Food C	Craving											
Eating Disorders	EDE-Q ELOCS	Self-Report	*		*	*	*	*		*	*	*
Eating Behavior	TFEQ YFAS	Self-Report	*			*	*	*		*	*	
Food Craving	Brief Questionnaire of Food Craving FCI-II	Self-Report	*	*		*	*	*	*	*	*	
Drive for Palatable Food	PFS Control of Eating Questionnaire	Self-Report	*	*		*	*	*	*	*	*	
Hunger	Hunger Ratings	Self-Report		*					*			
	Health and Behaviors	0 16 5	*		*	*	*	*	 	*	*	
Depression	Beck Depression Inventory-II	Self-Report	*	*	*	*	*	*	*	*	*	
Affect	Circumplex Scale	Self-Report		Î					Ŷ			+
Quality of Life	Perceived Stress Scale	Self-Report	*			-		*			*	*
Quality of Life	SF-12 Audit-2	Self-Report	*					*			*	
Alcohol Use	Godin Leisure Time Exercise Questionnaire	Self-Report	*					*			*	
Physical Activity Sleep		Self-Report	*	-		-		*			*	
Sieep	Pittsburgh Sleep Quality Index	Self-Report										
Safety & Compliance								 				
Adverse Events	SAFTEE Columbia Suicide Severity Rating Scale	Interview			*	*	*	*				
	Liver Function	Blood		*		*			*			

Page **12** of **49** 

Medication Compliance	Pill Counts	RA Count						*				
	Naltrexone and Bupropion levels	Plasma				*		*				
Vitals	Blood pressure and heart rate		*	*	*	*	*	*	*	*	*	
Placebo Rating	Placebo rating by clinician and participant	Self-Report				*		*				
Assays												
	Leptin, ghrelin, estrogen, progesterone	Blood		*					*			

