### Measures:

### **Screening Measures**

- MINI International Neuropsychiatric Interview-Version 7.0 (MINI) [57] is a brief structured interview for Axis I psychiatric disorders. Validation and reliability studies have supported the MINI, including good convergence with SCID [57]. The MINI requires much less time than the SCID and reduces participant burden while providing adequate psychiatric data to characterize patients and determine exclusion criteria.
- Eating Disorder Examination Interview—16th Edition (EDE) [58] is an investigator-based interview assesses the features of eating disorders and generates eating disorder diagnoses. The EDE will be our primary method for assessing binge eating and eating disorder psychopathology. The EDE focuses on the previous 28 days, except for diagnostic items, which are rated for additional duration stipulations to address *DSM*-5 criteria for BED. The EDE assesses the frequency of different forms of overeating, including objective binge-eating episodes (OBE; i.e., unusually large amounts of food with loss of control). The EDE also comprises four scales (dietary restraint, eating concerns, weight concern, and shape concern) and a global severity score. The EDE has good psychometric properties [59], is the major outcome measure for BED RCTs [44, 60], and has good test-retest reliability.
- Body Mass Index (BMI) will be calculated using measured Height (measured once at baseline) and Weight (obtained regularly at assessment meetings).
- Lipid profiles (**Lipids**): total cholesterol, HDL-, LDL-cholesterol, triglycerides will be obtained fasting per established protocols (Anderson et al., 1995).
- Glycemic Control: HbA1c, Glucose and Mean Plasma Glucose, routine measures of average glucose control for a previous (3-month) period.
- Hepatic function panel (**Liver Function**) will be assessed for safety at the first monthly treatment visit and at the end of treatment.
- Thyroid-stimulating hormone (TSH) will be assessed if patients report any history of thyroid disease or are taking thyroid medications.
- Urine drug testing for opiates will be completed for all participants.
- Urine pregnancy testing will be assessed for female patients of child-bearing potential.
- Menstrual Cycle Data: Menstrual cycle calendar (updated regularly), hormone use, reproductive and gynecological status

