### **Eating Behavior & Food Craving**

- Eating Disorder Examination-Questionnaire Version (**EDE-Q**). The self-report EDE-Q [61] generates the same overeating data and scale scores as the EDE interview. EDE-Q has good test-retest reliability with BED patients [59, 62, 63]. The EDE-Q converges well with the EDE as a measure of "change" [64].
- Eating Loss of Control Scale (**ELOCS**) [65] assesses the complexity of loss of control eating over the past four weeks. The ELOCS has demonstrated good convergent validity and is considered a valid self-report questionnaire that may provide important clinical information regarding experiences of LOC in people with BED and obesity.
- Three Factor Eating Questionnaire (**TFEQ**) [66] measures eating behaviors with 3 factors: cognitive restraint, disinhibition, and hunger. TFEQ has empirical support [67], and shows differential response across treatments consistent with putative mechanisms [68, 69].

- Yale Food Addiction Scale (YFAS) [70] is a measure of addictive eating behaviors with high fat/sugar foods. Items correspond to the substance dependence diagnostic criteria. The YFAS has demonstrated adequate internal reliability, convergent validity, and incremental validity in predicting binge eating.
- Brief Questionnaire of Food Craving is a measure food craving we developed based on a 10-item Tiffany Questionnaire of Smoking Urges [71] by replacing the word "a cigarette" with "food," and the word "smoke" with "eat."
- Food Craving Inventory (FCI-II) [72] assesses general and specific food cravings and comprises four subscales for different food groups. The FCI has been validated and psychometrically supported in studies with obesity and with obesity/BED groups [72, 73].

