### Procedures for providing follow up care:

Medical monitoring will occur at all clinic and follow up visits and medical care will be provided if warranted. If a study participant experiences any psychiatric symptoms or distress (e.g., depressive symptoms or

suicidality) at any stage of study participation he/she will receive short-term treatment and support from the study treatment team (including psychologists and a psychiatrist) and will be connected to a local emergency department (e.g., the Crisis Intervention Unit at Yale-New Haven Hospital) and his/her physician or therapist for ongoing care.

Measurement and reporting of subject accrual, adherence to inclusion/exclusion criteria.

Review of the rate of subject accrual and adherence to inclusion/exclusion criteria will occur regularly by the PI and co-Investigators and yearly by the DSMB. These reviews will help to assure that participants meet eligibility criteria and ethnic diversity goals outlined in the grant proposal.

Measurement and reporting of participant treatment completion rates.

Participation rates (retention and attrition) will be reviewed on an ongoing basis by the PIs and co-investigators to identify any potential problems, and formally by the PIs and DSMB semi-annually. Any differential dropout across blinded study groups and/or higher than expected dropout will be reviewed by the investigators to determine whether any problems are present and what, if any, corrective action needs to be taken.

During the reviews, if the DSMB has concerns about whether attrition has reached a level that might inhibit the ability of the study to address its primary aims, they will suggest a meeting to discuss methods for improving subject retention. Previous pharmacotherapy studies for BED (with comparable time frames for pharmacotherapy) have reported attrition rates between 20% and 38%. Studies of bupropion for obesity treatment reported attrition of 30% to 38%. Thus, "trigger points" for review and discussion by principal investigator and research staff will be: 35% ("low alert"), 40% ("mid alert"), 45% ("high alert"), 50% ("extreme alert"). With early alerts to problems, action would be taken to avoid higher level alerts; if a higher-level alert should arise, more drastic actions would be taken.

The following actions would be taken at each level of alert:

- (1) Low-level alert = Review of potential problems by PI.

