### 13. **Statistical Considerations:** Describe the statistical analyses that support the study design.

Baseline demographic and clinical characteristics for the randomized groups will be compared using chi-square tests for categorical variables, and ANOVA or Kruskal-Wallis tests for continuous variables. Continuous variables will be examined for normality using normal probability plots and Kolmogorov-Smirnov test statistics. If normality is not satisfied, transformations or nonparametric alternatives will be considered. Dropouts and completers will also be compared. Primary analyses will be based on an intent-to-treat basis. Primary outcomes will be tested at the two-sided alpha 0.05 threshold. Secondary analyses will be adjusted for multiple tests using the Bonferroni correction basing the adjustment on the number of conceptually related statistical tests within each hypothesis.

Overall analysis strategy. Mixed-effects models [92] will be used to compare treatments. These models allow for different numbers of observations per subject, use all available data on each subject, and are unaffected by randomly missing data. A further advantage is the capacity to test and account for individual-difference contributions to the treatment outcomes (Cudeck, 1996; Cudeck & Klebe, 2002; Hedeker et al., 1996; Hedeker & Gibbons, 1996; Singer, 1998). They provide flexibility in modeling the correlation structure of the data. In models for each outcome in Aims 1 & 2, we will include obesity status (obese vs. non-obese) and treatment (NB vs. placebo) as between-subject effects, time (see Aim-specific study time points) as a within-subjects factor, and subject as the clustering factor. Across analysis, time-points associated with the 12-week treatment phase will be considered as primary outcomes, and all analyses will be repeated to examine change

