during the 12-month follow-up period. All possible interactions will be modeled and the following primary a priori contrast will be tested: 1) placebo NB vs. active NB. Least-square means will be plotted and compared post-hoc to interpret significant effects. Because we cannot a priori predict the shape of the response over time in each arm of the trial we will first treat time as a categorical predictor and will then test for polynomial trends over time. We will consider different error structures (e.g., AR1, CS, independence) and select the best fitting one based on Schwartz' Bayesian Criterion (BIC). We will compare dropout patterns between groups and if there are concerns of informative dropout or informative intermittent missing data, we will use pattern mixture models [93] to perform sensitivity analyses. Secondary models will include subjects with complete data. To test for assessment reactivity, we will evaluate whether biosensor assessment (yes/no; between-subject variable) moderates our primary outcomes in Aim 1 (as either a main effect, or interacting with medication). If this is found, then all subsequent analyses for Aims 1 & 2 will be limited to the sample (n=140) without the biosensor assessment.

Primary Aim 1. We will use the mixed models described above to test the effectiveness of NB medication for BED patients with and without obesity. The primary aims are to evaluate NB medication for (a) reducing binge eating frequency; and (b) in the patients with obesity, for reducing % weight loss. Significant NB main effects (regardless of obesity status) on frequency of binge eating will be considered supportive of our primary hypothesis. We also expect that NB will be associated with significantly greater reductions in % weight loss among the BED+obese group. In view of the factorial design, we will also be able to assess whether obesity status moderates reductions in binge eating frequency. These analyses will focus on 12-week outcomes. Secondary analysis will be repeated to examine change during the 12-month FU period.

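### The EDE is given only once after baseline in the 12-week phase, so the primary mixed model has no on-treatment value for anyone who misses month 3, and interim EDE-Q binge counts are not assigned to the primary analysis

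*Combined protocol and SAP*

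**What the plan says.** The Overview of Study Design (Section I, item 4) says "The primary outcome measure is reduction in binge-eating frequency" without naming an instrument. Under Screening Measures the plan does name one: "The EDE will be our primary method for assessing binge eating and eating disorder psychopathology". It adds that "The EDE focuses on the previous 28 days".

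In Figure 2 the row "EDE Interview" is marked at baseline, month 3, 6 months and 12 months. The EDE-Q row is marked at baseline, week 2, months 1, 2 and 3, and both follow-ups. Under Eating Behavior & Food Craving, the EDE-Q is said to be an instrument that "generates the same overeating data and scale scores as the EDE interview".

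Statistical Considerations (item 13) makes the 12-week time points primary and justifies mixed models in these words: "These models allow for different numbers of observations per subject, use all available data on each subject, and are unaffected by randomly missing data". On the shape of response, "we will first treat time as a categorical predictor and will then test for polynomial trends over time", and the error structure (AR1, CS or independence) is to be picked by BIC. Aim-specific time points are mentioned but Aim 1 lists none. Pattern-mixture models are planned if informative dropout is suspected. The EDE-Q appears in item 13 only under Secondary Aims, where its repeated scales supply change variables for mediation.

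**The concern.** The model is described as if the primary outcome were a series, but within the primary window the named instrument gives one on-treatment value. The usual argument for a mixed model is that early on-treatment readings from people who later leave inform their missing final value. With the EDE there are no such readings.

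What is at stake is the NB-versus-placebo contrast in binge eating. If, for example, placebo participants leave because they are still bingeing while NB participants leave for unrelated reasons, a model that knows only their baseline cannot see the difference. The EDE-Q counts that would show it are already being collected.

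**Working it through.** **Schedule against model.** In 12 weeks there is one post-baseline EDE and four post-baseline EDE-Q readings. With two EDE time points (baseline, month 3):
- only a straight line fits, which is the same as categorical time, so there are no higher polynomial trends to test;
- AR1 and CS both reduce to a single correlation, so BIC cannot choose between them (independence remains distinct).

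**How many could be affected.** For earlier BED drug trials the plan says they "have reported attrition rates between 20% and 38" per cent. Applied to N = 200: 0.20 × 200 = 40 and 0.38 × 200 = 76. These counts assume similar attrition here and nobody returning for month 3.

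**What baseline-only participants contribute.** Take unit variance, 100 per arm, m = 100(1 − d) observed at month 3, and baseline-to-month-3 correlation r (assumed 0.3 to 0.7). Per-arm variances of mean change:
- completers only: 2(1 − r)/m
- likelihood with baseline-only participants kept: (1 − r²)/m + (1 − r)²/100

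At d = 0.20, r = 0.3: 1.4/80 = 0.0175 against 0.91/80 + 0.49/100 = 0.0163, a 7% reduction. Over r = 0.7 to 0.3 the reduction is 3–7% at 20% missing and 6–13% at 38%. For a baseline-adjusted (ANCOVA-type) contrast they add nothing.

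**What interim readings add to precision.** Let R0² be the share of month-3 variance explained by baseline and R1² the share explained once interim readings are added:
- without interim: (1 − R0²)/m
- with interim: (1 − R1²)/m + (R1² − R0²)/100

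Example at 38% missing, baseline correlation 0.3, interim correlation 0.5, month-1 reading only: R0² = 0.09; R1² = (0.09 + 0.25 − 2 × 0.3 × 0.5 × 0.3)/(1 − 0.09) = 0.275. The variances are 0.91/62 = 0.0147 and 0.725/62 + 0.185/100 = 0.0135, so omitting the reading costs 8%. Over assumed interim correlations of 0.5 to 0.85, using month 1 or months 1 and 2, the excess is 4–17% at 20% missing and 8–37% at 38%.

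**Bias by simulation.** Assumptions: true month-3 difference 0.50 SD; month-3 EDE correlates 0.30 with baseline, 0.50 with month-1 EDE-Q and 0.65 with month-2 EDE-Q; logistic dropout on month-2 bingeing with slope 1 per SD; every leaver has month-1 and month-2 EDE-Q values. Month-3 means come from within-arm regression. R² is 0.09 from baseline alone and about 0.44 with the EDE-Q added.

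| Missing in each arm | Placebo dropout response-driven, NB random: baseline + month-3 EDE | Same, EDE-Q months 1–2 added | Both arms response-driven: baseline + month-3 EDE |
|---|---|---|---|
| 20% | 0.40 | 0.50 | 0.50 |
| 30% | 0.36 | 0.50 | 0.50 |
| 38% | 0.32 | 0.50 | 0.50 |

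Variations:
- With slope 2, the second column becomes about 0.35, 0.29 and 0.24.
- If half the leavers go before month 1, the corrected estimates are about 0.46, 0.44 and 0.43.
- In a separate set-up (true effect 0.40 SD, dropout on the month-1 value, same slope in both arms), unequal rates of 38% placebo and 20% NB shrink the effect by 0.06–0.07 SD. Reversing the rates inflates it by about 0.07 SD. Adding the month-1 reading brings the bias close to zero.

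**The case against.** The strongest reply has five parts.

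- **The analysis text is generic.** Item 13 covers every outcome in Aims 1 and 2. Weight is measured at every treatment visit, and the EDE has four points once follow-up is included, so polynomial trends and error structures are meaningful there. This stands: the mismatch is confined to EDE binge eating in the 12-week window.
- **A reader might infer that baseline-only participants contribute nothing and that the EDE-Q is ignored.** The documents do not support either. Such participants trim variance slightly and cover dropout that depends on baseline, and Secondary Aims uses repeated EDE-Q scales for mediation. What is missing is a role in the primary analysis.
- **A reader might take 40–76 missing as a forecast.** It is not. The plan cites attrition in earlier trials to set alert levels. Dropouts are invited to follow-up evaluations, the end-of-treatment assessment is paid, and participants considered for medication discontinuation because of adverse effects are asked to keep attending clinic visits. These steps may lower the number, but none is a stated procedure for obtaining a month-3 EDE from everyone who stops, and the later EDEs are off treatment.
- **A reader might say that pattern-mixture models cannot be identified here, or that the primary result is left to be picked after unblinding.** The first is too strong: explicit restrictions, such as delta adjustment, work with one post-baseline value, although the plan states none. The second is not shown either, because Screening Measures names the EDE. The gap is that Aim 1 does not repeat the instrument or list its visits.
- **The simulated recovery to 0.50 is built in**, because dropout was made to depend on a reading that then enters the model. This stands: the table shows what can happen, not what will.

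**Conclusion.** The point holds in limited form. For the primary binge-eating outcome the mixed model's missing-data advantage is largely absent within 12 weeks, and available on-treatment binge counts have no assigned role in the primary analysis. This is a weakness of method that is cheap to repair, not a demonstrated bias.

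The size depends on how dropout works. The contrast drops from 0.50 to about 0.40–0.32 SD if only placebo dropout follows on-treatment bingeing, and is unbiased if both arms share the mechanism at equal rates. It can be inflated if response-driven loss is heavier on NB. The correlations, effect size and dropout model are assumptions; the plan gives no effect size, SD or EDE/EDE-Q coefficient. Correction by EDE-Q works only if data are missing at random given the interim values and the two instruments agree adequately.

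**What to change.** 1. In Aim 1, name the primary endpoint as EDE objective binge episodes over the 28 days before month 3, and list its time points.
2. Handle missing month-3 EDE values by multiple imputation within arm, or a joint likelihood model, using baseline EDE and EDE-Q binge counts at baseline and whichever of months 1–3 are available.
3. Move the time-shape analyses for binge eating to the EDE-Q series.
4. Pre-specify a delta-adjusted or reference-based sensitivity analysis on the month-3 EDE.
5. The plan states a 28-day window for the EDE but none for the EDE-Q. If the EDE-Q shares it, about 14 of the 28 days covered at week 2 precede treatment (28 − 14 = 14). Do not then treat that reading as fully on-treatment; it may still serve as an auxiliary variable.

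The cost is SAP wording and modest programming, with no new visit, instrument or participant. The downside is that an imputation model must be specified and defended, and it helps less for people who leave before month 1.
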